8.2.1. Inclusion criteria

Patients must meet all of the following inclusion criteria to be eligible for inclusion in the study:

1. A diagnosis of metastatic breast cancer, based on the National/MHS cancer registry.
2. Newly diagnosed metastatic breast cancer patients and newly treated with palbociclib within 6 months of diagnosis, in any line of treatment in the metastatic setting.
3. Available data on palbociclib treatment for at least 6 months.
4. Continuous healthcare plan enrolment in MHS for at least one year before index date.
5. At least 18 years of age at index date.

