7. RESEARCH QUESTION AND OBJECTIVES

Primary Objective: To describe patient demographics, clinical characteristics, clinical outcomes and treatment patterns of adult breast cancer patients who have initiated palbociclib combination treatment as per the national basket of health services in January 2018 until August 2020 for all lines of therapy. Extended follow up for treatment patterns to 30th June 2022.

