8. RESEARCH METHODS

8.1. Study design

This is a population based retrospective database study that will include patients with metastatic, HR+/ HER2- breast cancer and who initiated first or subsequent lines of treatment with palbociclib. Data will be available from Maccabi Healthcare Services (MHS) database in Israel for patients who received approval for treatment with palbociclib since 01 January 2018 until 31 August 2020.

Treatment amendment and extension: Treatment lines will be rerun for the same patient cohort for an additional year and a half of follow-up to 30 June 2022.

The database review followed by a medical record review will capture data from approximately 500-700 patients on demographics, clinical characteristics, disease history, treatment history, palbociclib dosing, clinical outcomes and post-palbociclib combination therapy treatment data. The study will be descriptive in nature therefore no control or comparator groups will be included.

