- Number (N) (%) patients receiving first, second- and third-line treatments by drug name and therapeutic group, median duration of each line of therapy, and number of cycles for each line of therapy. Treatment lines are defined according to the sequence of dispensed medications, with information captured both from pharmacy database (for medications approved by the HMO), and from hospital medical records (including information on medications provided by private insurance and clinical studies) using the following algorithm. Any drug purchased within 1 month of a new line is considered part of that line. Cessation of a drug from a combination regimen is considered the same line as the patient is not receiving additional treatment. Cessation is likely due to tolerance issues or adverse effects although we do not know the reason as our data is from purchase data. Addition of a new drug to a current regimen is considered a new treatment line.
- Index treatment regimen - palbociclib combination partner: Aromatase Inhibitors (AI) or fulvestrant; Subsequent therapy per lines of therapy.
- Dosing and dose changes, interruptions, delays, and discontinuations associated with palbociclib therapy.
- Treatment lines will be rerun for extended follow up to 30 June 2022.

8.3.4. Cancer related variables:

These variables will be extracted from patient PDF files/ letters sent to MHS from the physician.

- Date of initial breast cancer diagnosis.
- Histology.
- Location of metastases: bones, brain, visceral, lymph nodes, other.

- ECOG performance status at diagnosis.
- Molecular status data: performed HER2/ HR tests (yes/no).
- Hormone sensitivity: primary or secondary resistance.
- Progression of disease from imaging.

8.3.5. Clinical outcomes for palbociclib (analysed separately by therapy line):

- N (%) progression at 6, 12 and 24 months.
- Duration of treatment on palbociclib (Median time on treatment).
- Time on treatment for subsequent line of therapy.
- Time to chemotherapy after palbociclib treatment.

■ CCI [REDACTED]

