8.5. Study size

Sample size calculations are not applicable as this is a descriptive study. The expected number of patients eligible for the study is about 500-700 patients.

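### Criterion 2 limits every line to palbociclib started within 6 months of diagnosis, so second- and third-line patients are a selected subset that the objective, design and bias statement do not disclose

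*Combined protocol and SAP*

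**What the plan says.** Section 8.2.1 requires every inclusion criterion to be met. Criterion 2 asks for newly diagnosed metastatic patients "newly treated with palbociclib within 6 months of diagnosis, in any line of treatment in the metastatic setting".

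The window between diagnosis and palbociclib appears nowhere else:

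- **Section 7** defines the adults to be described in these words: "initiated palbociclib combination treatment as per the national basket of health services in January 2018 until August 2020 for all lines of therapy".
- **Section 8.1** describes patients with metastatic HR+/HER2- disease "who initiated first or subsequent lines of treatment with palbociclib". It adds, for the extension: "Treatment lines will be rerun for the same patient cohort".
- **Section 8.2** has a 6-month rule, but it concerns follow-up on palbociclib, as criterion 3 does. That is a different requirement.
- **Section 8.9** concedes that the observational design leaves the study open to selection bias. It then argues that this bias is kept small because the intention is to capture every metastatic patient MHS treated in the period.

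Lines are built from dispensing records (section 8.3.3): "Any drug purchased within 1 month of a new line is considered part of that line", and "Addition of a new drug to a current regimen is considered a new treatment line".

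Section 8.3.5 analyses palbociclib outcomes by therapy line. Annex 1 Tables 1 and 2 have first-, second- and third-line columns. Annex 1 Table 3 puts a log-rank P value beside time on palbociclib by line, although section 8.7 names no log-rank test. On size, section 8.5 says only: "The expected number of patients eligible for the study is about 500-700 patients".

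**The concern.** A single 6-month window, applied to every line, does not act equally on every line. A first-line patient has only to start palbociclib soon after diagnosis. A second-line patient must also have had a short first line, and a third-line patient must have passed through two lines in the same 6 months. Such patients can be described, but they do not represent second- and third-line palbociclib use in general.

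The main product of a descriptive study is an accurate account of who was studied. If the plan is followed as written, the report would carry second- and third-line results under an all-lines label. It would also repeat a reassurance about selection bias that the entry rule undercuts.

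**Working it through.** **1. The texts side by side.** The objective covers everyone starting palbociclib from 1 January 2018 to 31 August 2020, in any line. Criterion 2 covers only those who start within 6 months of diagnosis. Anyone with metastatic disease diagnosed before 1 July 2017 who starts on or after 1 January 2018 fits the objective and fails the criterion. This needs no assumption beyond reading the diagnosis in criterion 2 as the metastatic one, which its opening words support.

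**2. Who can enter in a later line.** Under the section 8.3.3 rules there are three routes within 6 months:

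- the earlier line or lines ended early;
- they were switched early;
- palbociclib was added more than 1 month after endocrine therapy began, which counts as a new line without any failure.

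**3. Illustrative size.** The plan gives no figure to reproduce: 500-700 is an expected total without inputs, and no earlier-line duration is stated. I assume that:

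- the first metastatic line starts at diagnosis;
- its duration is exponential with median M months, so λ = ln 2 / M;
- palbociclib follows at once;
- diagnoses occur at a constant rate from H months before January 2018 to August 2020.

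The objective's period is 32 months. Among second-line starts in that period, the share meeting the window is

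share = 32(1 − e^(−6λ)) / [32 − e^(−λH)(1 − e^(−32λ))/λ].

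For M = 12 and H = 36: λ = 0.0578. The numerator is 32 × 0.2929 = 9.37. The denominator is 32 − 0.125 × 0.8425/0.0578 = 30.18. The share is 31%.

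| Earlier-line median (months) | H = 36 | H = 60 | Limit for large H, 1 − e^(−6λ) |
|---|---|---|---|
| 6 | 50% | 50% | 50% |
| 12 | 31% | 30% | 29% |
| 24 | 21% | 18% | 16% |

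For third line with two earlier lines of equal median, the large-H limit is 1 − e^(−6λ)(1 + 6λ): 15%, 4.8% and 1.3% for medians of 6, 12 and 24 months.

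**4. Dependence on the denominator.** If only patients diagnosed in 2018-2019 are counted, the second-line share is (1 − e^(−6λ)) / [1 − (e^(−8λ) − e^(−32λ))/(24λ)], which gives 58%, 44% and 37% for medians of 6, 12 and 24 months. Those figures already assume a newly diagnosed cohort, so they do not measure the gap against the objective.

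**5. Dependence on add-ons.** Suppose a fraction p of second-line starts are add-ons, all made inside the window, and 30% of the rest qualify (M = 12). The qualifying share is q = p + 0.30(1 − p), and add-ons form p/q of those who enter. For p = 10%, 25% and 50%, q is 37%, 47.5% and 65%, and p/q is 27%, 53% and 77%. Both the size and the make-up of the second-line group therefore depend on a number that the plan does not ask to have reported.

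**The case against.** The strongest reply is that this is ordinary narrowing. Objectives and design summaries rarely repeat each entry rule, section 8.2 refers the reader to the inclusion list, and the window is stated openly there. Annex 1 Table 1 is titled for patients diagnosed in 2018-2019, which suggests that a newly diagnosed cohort was intended. On that reading the design is coherent. Section 8.9 also admits selection bias in general, warns of wide intervals in small strata and disclaims causal inference.

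Much of this stands. Silence in sections 7 and 8.1 is not by itself a contradiction, and the window may be deliberate. But none of the caveats names the window, and the reason section 8.9 gives for the bias being small is one that criterion 2 contradicts. If the cohort is meant to be newly diagnosed, the objective, the design and section 8.9 still have to say so.

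A second reply is that the authors may have meant the 6-month limit for newly diagnosed patients and entry in any line as a separate route. The sentence does not say that, and doubt about who is eligible needs settling in any case.

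A third is that comparing lines is confounded with or without the window. That is correct. The window adds an eligibility difference to a comparison that was already unsound, so it is not the only reason to drop the P value.

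**Conclusion.** The point holds as a mismatch between the eligibility rule and the description of the population, and it should be corrected before by-line results are reported. Confidence in the mismatch is high and rests on the text, with the window read as running from metastatic diagnosis. The shares of about 50%, 30% and 20% for second line are illustrations. They depend on exponential durations, immediate start of palbociclib, a constant diagnosis rate and 36 to 60 months of earlier diagnoses, and they leave add-ons out.

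A reader might infer three stronger things that the documents do not support:

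- **That later-line outcomes will look worse than they should, because early failures are over-represented.** Add-on patients enter without failure, their number is unknown, and nothing in the documents links earlier-line duration to time on palbociclib. The net direction cannot be determined.
- **That the window is a mistake or the design invalid.** The Annex 1 Table 1 title points to a deliberate newly diagnosed cohort, which is a legitimate choice if it is described as such.
- **That the later-line groups will be too small to use.** Only a total is given, so their size is unknown.

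**What to change.** Reconcile criterion 2 with sections 7, 8.1 and 8.9.

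If the window is intended:

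1. Describe the population in the objective, design and table titles as patients starting palbociclib within 6 months of metastatic diagnosis.
2. Replace the section 8.9 sentence saying selection bias is minimised, and name the window as a limitation on the second- and third-line results.
3. Report by line the time from metastatic diagnosis to index and the number entering a later line by add-on. Add the metastatic diagnosis date, with its source, to the variable list.
4. Present the lines descriptively and drop the by-line log-rank P value from Annex 1 Table 3.

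This costs text edits, two descriptive rows and one test, and it narrows the stated conclusion. It should not be called free of data work. Sections 8.3 and 8.3.4 list only the date of initial breast cancer diagnosis, and section 8.3 notes that those records may be incomplete. The metastatic date is needed to apply criterion 2 at all, so the extra burden should be small, but the plan does not show that it is collected.

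If the window is not intended for later lines, reword the criterion so that it applies only where meant. This is the dearer route: it needs chart extraction for additional later-line patients and changes the cohort that section 8.1 says will be carried unchanged into the extension.

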8.2. Setting

Patients (age \geq 18 years) will be identified from MHS purchase data between 01 July 2017 until 31 August 2020.

Index date will be defined as date of initiation of palbociclib treatment.

Patient records must meet the following criteria to be eligible for the medical record reviews. Patients must be at least 18 years of age at index date and they must have been diagnosed with HR+/HER2- ABC/ MBC. Patients must have received palbociclib combination in line with Israel approved indications. A minimum of 6 months follow up of palbociclib combination therapy prior to date of medical record review will be necessary for inclusion. This will permit the capture of meaningful clinical outcomes data. Patients will be followed through the end of the observation period, date of death or left the health maintenance organization (HMO).

A full list of the inclusion criteria can be found in Section 9.2.1.

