Index palbociclib treatment dose schedule change	MHS structured data	Treatment characteristic	Study observation period	Reported	Proportion of patients with dose changes
Date of treatment initiation	MHS structured data	Treatment characteristic	Study observation period	Not Reported	First date will be used if a regimen consists of more than one drug given on different dates.
Index treatment end date	MHS structured data	Treatment characteristic	Study observation period	Not Reported	Date of final treatment for each drug or regimen. It is possible that the patient's treatment stop date is not documented if the patient dies, is lost to follow up or is still on therapy. The final treatment date death date or end of

					study date will be used, whichever is earliest.
Variable	Source	Role in study	Period of measurement	Reporting phase	Operational definition
Post-palbociclib treatment duration	MHS structured data	Clinical Outcomes	Study observation period	Not Reported	
The regimen received by patients following discontinuation from the palbociclib treatment.
 
The duration (in weeks) between the start and stop of the post-palbociclib treatment. Findings will be summarized as the mean (\pm SD) and median (range) of values.

					subsequent treatment for unknown reasons
Time to chemotherapy after palbociclib treatment	MHS structured data	Clinical Outcomes	Study observation period	Reported	Time to chemotherapy (Kaplan Meier method median (95% CI)) from end of index treatment and start of chemotherapy. Summary of number of events and censored patients at 6, 12, 18, 24 months.
Time to next treatment (TTNT)	MHS structured data	Treatment characteristic	Study observation period	Reported	TTNT will be defined as the interval (in weeks or months) between the start of the index treatment date and the date of the next-line treatment. Patients who did not advance to the next treatment will be censored on the study end date or death, whichever occurs first. Kaplan-Meier (K-M) method with 95% CI and summary tables of

					events and censored patients at 6, 12, 18, 24 months.
CCI					

8.3.1. Demographic characteristics at baseline (from structured electronic database):

- Patient demographics: age, age group and gender.
- Region of residence (North, Central, South).

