ANNEX 1. LIST OF STAND ALONE DOCUMENTS

1. Baseline demographic and clinical characteristics of patients diagnosed with metastatic breast cancer 2018-2019 split by Palbociclib as first-, second- or third line (n=XX).

		First Line	Second Line	Third Line	Total n=XXX

Demographic Variables					
Age	median (IQR)				
	<65				
	≥65				
Gender	male				
	female				
Region of residence	Central				
	North				
	South				
Socioeconomic status*	low				
	medium				
	high				
Clinical Variables					
Deyo-Charlson Comorbidity Index (without malignancy or HIV)	mean (SD)				
	0				
	1				
	2				
	3				
	≥4				
Co-morbidities	Diabetes mellitus				
	Cardiovascular disease				
	Stroke				
	Congestive heart failure				
	Hypertension				
	Chronic kidney disease				

	Chronic obstructive pulmonary disease			
	Other (e.g. depression)			
Co-medications				
Smoking	Ever smoker			
	Never smoker			
	Unknown			
BMI				
Menopausal status	Pre/Peri menopausal			
	Postmenopausal			
Genetic counselling for gBRCAm	Yes			
	No			
Testing for gBRCAm	Yes			
	No			

2. Cancer related characteristics of patients with breast cancer at baseline

		First Line	Second Line	Third Line	Total (n)
Histology					
Location of metastases	Brain				
	Bone				

	Visceral				
	Lymph nodes				
	Other				
ECOG	0-1				
	2				
	3-4				
	Unknown/missing				
Hormone sensitivity	Primary				
	Secondary				
Molecular status data: performed HER2 / HR tests	HR+ [Estrogen Receptor positive (ER+), Progesterone Receptor positive (PR+) or both]				
	HER2+				

3. Time on Palbociclib treatment

Line of treatment (first-, second- or third line)	N	Number (%) discontinued	Median time on treatment (95% CI), months	% on treatment at 3 months	% on treatment at 6 months	% on treatment at 12 months	% on treatment at 24 months	Log rank P value

4. Palbociclib treatment patterns

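### The six-month inclusion rule depends on events after palbociclib start: read literally it drops early deaths and leavers, and neither its meaning nor its cut-off date is stated

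*Combined protocol and SAP*

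**What the plan says.** Section 8.2.1 lists criteria that must all be met. The third is "Available data on palbociclib treatment for at least 6 months". Section 8.2 gives the matching rule: "A minimum of 6 months follow up of palbociclib combination therapy prior to date of medical record review will be necessary for inclusion". Neither place says what happens to a patient who stops palbociclib, dies or leaves MHS before month 6.

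The time origin is clear: "Index date will be defined as date of initiation of palbociclib treatment". The same section ends follow-up at the close of the observation period, at death, or on leaving the HMO. In 8.3, TTNT runs between "the start of the index treatment date and the date of the next-line treatment", and "Patients who did not advance to the next treatment will be censored on the study end date or death, whichever occurs first". The rule for the index treatment end date in 8.3 allows the date of death to serve as the end of treatment.

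Time on palbociclib is a listed clinical outcome (8.3.5). Table 3 of Annex 1 reports it by line of therapy, as a median and as the percentage "on treatment at 3 months" and at 6, 12 and 24 months. Section 8.9 says that selection bias is kept small because the study sets out to take in all treated metastatic patients.

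**The concern.** A cohort whose clock starts at initiation should not be selected on what happens in the following six months. If it is, patients who fail early are removed from the group in which failures are counted, and the on-treatment curve is too high.

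Three readings of the six months are open:

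- **Calendar:** initiation took place at least six months before record review, whatever happened next.
- **Observed follow-up:** the patient was alive and enrolled for six months.
- **On drug:** the patient took palbociclib for six months.

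Only the first leaves early failures in. Treatment is derived largely from purchase records (8.3.3), so a programmer given criterion 3 alone could reasonably require six months of purchases. A reader of the report could not tell which cohort Table 3 describes, nor compare it with other palbociclib cohorts. The extension to 30 June 2022 uses the same patients (8.1), so any selection carries into it.

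**Working it through.** **Planned figure.** There is none to reproduce. Section 8.5 says a sample size calculation does not apply, and the documents give no expected median, early death rate or gap to next treatment. The medians, loss rates and distribution shapes below are assumptions, and the results are illustrative.

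**Step 1: passages side by side.** Time zero is initiation (8.2), and the six-month condition is met or failed after it (8.2, 8.2.1). Follow-up stops at death or leaving (8.2), so a patient who dies in month 3 has three months of follow-up and fails a six-month minimum taken at its word. The visible text of 8.7 (partly redacted) has no landmark and no delayed entry.

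**Step 2: observed-follow-up reading.** Let q be the share of initiators removed, all counted as off treatment by month 6. For t of 6 months or more, the retained patients show S(t)/(1 − q). With S(t) = 2^(−t/m) and m = 12, S(6) = 70.7% and S(12) = 50.0%. The median is −12·log2[0.5(1 − q)].

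| Assumed q | On treatment at 6 months | At 12 months | Median (true 12) |
|---|---|---|---|
| 2% | 72.2% | 51.0% | 12.3 |
| 5% | 74.4% | 52.6% | 12.9 |
| 10% | 78.6% | 55.6% | 13.8 |

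Leaving adds little. Section 8.4 gives under 1% a year, so at most 1 − 0.99^0.5 = 0.5% in six months, which moves 70.7% to no more than 0.707/0.995 = 71.1%. Even that is an upper bound, since 8.7 censors leavers. The size therefore depends on early deaths, which the documents do not quantify.

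**Step 3: on-drug reading.** The retained curve is S(t)/S(6) from month 6 and 100% before it. For a Weibull with true median m and shape k, S(t) = 2^(−(t/m)^k). Setting S(t) = S(6)/2 gives a conditional median of (6^k + m^k)^(1/k), which is m + 6 when k = 1. The first four result columns use k = 1.

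| True median m | Dropped | At 3 months | At 6 months | At 12 months | Median, k = 1 | k = 1.3 | k = 0.8 |
|---|---|---|---|---|---|---|---|
| 6 | 50.0% | 70.7 → 100% | 50.0 → 100% | 25.0 → 50.0% | 12.0 | 10.2 | 14.3 |
| 12 | 29.3% | 84.1 → 100% | 70.7 → 100% | 50.0 → 70.7% | 18.0 | 15.6 | 21.2 |
| 24 | 15.9% | 91.7 → 100% | 84.1 → 100% | 70.7 → 84.1% | 30.0 | 27.0 | 34.3 |

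The rise is 6 months if exponential, 3.0 to 4.2 for k = 1.3 and 8.3 to 10.3 for k = 0.8. The direction is upward throughout.

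**Step 4: TTNT.** Under the on-drug reading, patients who stopped and moved on early are missing, so TTNT is biased upward. The amount cannot be fixed, because it depends on the gap between stopping and the next line. There is no strict six-month floor either: 8.3.3 counts adding a drug to the current regimen as a new line. Under the observed-follow-up reading, deaths are censored, so removing them changes little if death is independent of the next line. Patients who start a next line and then die before month 6 are the exception.

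**Step 5: calendar reading.** Early failures stay in and this bias does not arise, but the cohort depends on an unstated date. The approval window in 8.1, 1 January 2018 to 31 August 2020, is 974 days. Assuming even accrual:

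- Review on 8 November 2020, the start of data collection (section 5): index dates after 8 May 2020 are excluded, 115/974 = 11.8%.
- Cut-off 31 December 2020, inferred from the year-and-a-half extension in 8.1: index dates after 30 June 2020 are excluded, 62/974 = 6.4%.
- Cut-off 30 June 2022: none, since the last index date is 21.9 months earlier.

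**The case against.** The strongest reply is that calendar time was plainly meant. Table 3 plans on-treatment percentages at 3 and 6 months, which would be pointless if everyone had to be on drug for six months. Section 8.2 ties the six months to the time before record review and foresees follow-up ending in death, and 8.9 aims to include all treated patients. A reader might infer from criterion 3 that the protocol requires six months on palbociclib, and hence that its median is overstated by six months. The documents do not support that: the on-drug reading fits Table 3 worst, and the exact six months comes from the exponential assumption alone.

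That reply limits the claim but does not remove it. No sentence states the calendar reading, criterion 3 omits the reference to record review, and the review date is undefined within a collection period running from 8 November 2020 to 30 June 2022. Taken at its word, a six-month minimum of follow-up that ends at death excludes early deaths.

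It is also fair that 8.9 opens by admitting the study is prone to selection bias, so its later sentence needs qualifying under a survival or on-drug rule but is not a flat contradiction. The observed-follow-up result relies on death ending treatment, and the 8.7 sentence on these analyses is partly redacted. The study is descriptive, without a comparator. Even so, a descriptive estimate depends on who is counted.

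**Conclusion.** The point stands as a rule that should be rewritten, not as a demonstrated inflation of results. Six months of data or follow-up after index is a stated condition of inclusion, while the outcomes are timed from index. Applied literally, it removes early deaths and leavers and gives a small favourable bias in time on treatment, of unknown size. The 12.3-13.8 month range rests on a true median of 12 months, exponential times and 2-10% early loss, none of which the documents supply. Only if the rule is run as six months on drug does the bias become large, with two columns of Table 3 fixed at 100% and the median raised by roughly 3 to 10 months over the medians and shapes tried. TTNT would then also be too long, by an amount that cannot be stated. Confidence is high that the text leaves this open, but the documents do not establish which rule will be run. It should be fixed before the cohort is drawn or reported.

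**What to change.** In 8.2 and 8.2.1, replace the condition with: *palbociclib initiation recorded in MHS data, with an index date at least 6 months before [one stated cut-off date], regardless of whether the patient stopped palbociclib, progressed, died or left MHS in that period.* Report the number of initiators excluded by the rule.

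If a survival or on-drug condition is really intended, label the cohort in the tables as conditional on it and qualify the selection-bias sentence in 8.9. For an on-drug condition, also start time on treatment and TTNT at a month-6 landmark and drop the 3- and 6-month columns from Table 3.

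The cost is one sentence in two places and one date. There may be some extra chart extraction for patients who would otherwise have been left out, but no new data source. The figures may turn out less favourable if a stricter rule was in mind. If calendar time was meant all along, only the wording changes.
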